5. STATISTICAL ANALYSES

5.1. Demography

5.1.1. Analysis of demographics/baseline characteristics planned in the protocol

Demographic characteristics (age at first study vaccination in years, gender and Geographic Ancestry/ethnicity), 'time since previous HZ episode', age stratum and withdrawal status will be summarized by group using descriptive statistics:

Frequency tables will be generated for categorical variable such as age stratum, 'time since previous HZ episode' and gender.

Mean, median, Standard Deviation (SD) will be provided for continuous data such as age.

The analysis will be based on ES.

5.1.2. Additional considerations

- Demographic characteristics (age at first study vaccination in years, gender, ethnicity, and race), 'time since previous HZ episode' and age stratum will also be generated on mES, PPS-HI and ~~CCI~~ [REDACTED]
- The numbers of withdrawn subjects will be tabulated according to the reason for withdrawal on ES and mES.
- Number of subjects by country and center will be presented on ES.

The following table will be generated for web disclosure:

- Percentage of Enrolled subjects by country will be tabulated by group,
- Percentage of Enrolled subjects in the following age strata ≤ 64 , $65-84$, ≥ 85 YOA will be tabulated by group.
- Summary of important protocol deviations leading to elimination will be presented from Enrolled Set.
- The number of subjects enrolled into the study as well as the number of subjects excluded from PPS analyses will be presented through tables.

5.2. Exposure

5.2.1. Analysis of exposure planned in the protocol

None

5.2.2. Additional considerations

The number of doses administered will be tabulated on ES.

5.3. Analysis of incidence rate of Herpes Zoster recurrence

5.3.1. Analysis of incidence rate of Herpes Zoster recurrence planned in protocol

The primary analysis of incidence rate of HZ recurrence will be based on the mES. The same analysis will be performed on ES to complement the mES analysis.

5.3.1.1. Within group

For each group, the number of subjects, person-time, number of confirmed HZ cases and incidence rate will be tabulated from 30 days post the last vaccination until study end and from first study vaccination until study end on ES.

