● is used to indicate a study procedure that requires documentation in the individual eCRF.

○ is used to indicate a study procedure that does not require documentation in the individual eCRF.

 Only for women of child bearing potential. Please refer to [glossary of terms](#) for definition of woman of child bearing potential.

 Diary card to collect solicited and unsolicited AEs following each vaccination and HZ specific diary card.

 Subjects will be instructed to contact their study site immediately if he/she manifests any symptoms he/she perceives as serious and in case of pregnancy or HZ symptoms.

 Before vaccine administration

 Any subject with a clinically diagnosed suspected HZ episode between Visit 1 (Day 1) and Visit 2 (Month 2) is not to receive the second dose.

 The duration of the study will vary for each subject. Study conclusion will be scheduled based on the projected date of the last contact of the last enrolled subject, that is 26 months (790 days) from the enrolment date. The study conclusion visit/ contact for subjects with an ongoing episode of HZ will occur after a 4-week pain-free period is documented OR after Day HZ-92 follow-up has been completed.

 Refer to Section [4.5](#) and [Table 8](#) for the brief evaluation and study procedures to be followed in case of suspected HZ.

\* For the last enrolled subject only

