## 7.5. Contraindications to subsequent vaccination

The following events constitute absolute contraindications to further administration of study vaccine. If any of these events occur during the study, the subject must not receive additional doses of vaccine but may continue other study procedures at the discretion of the investigator (see Section 9.5).

- Anaphylaxis following the administration of vaccine
- Pregnancy (see Section 9.2.1)
- Any SAE judged to be vaccine-related by the investigator.
- Occurrence of HZ between the first and second vaccine dose.
- Any confirmed or suspected immunosuppressive or immunodeficient condition, including Human Immunodeficiency Virus (HIV) infection.
- Any condition that in the judgment of the investigator would make intramuscular injection unsafe.
- Occurrence of a new pIMD or the exacerbation of an existing pIMD that, in the opinion of the investigator, expose the subject to unacceptable risk from subsequent vaccination. In such cases, the investigator should use his/her clinical judgement prior to administering the next dose of the vaccine. Refer to Section 9.1.5.1 for the definition of pIMDs.

The following events constitute contraindications to administration of study vaccine at that point in time; if any of these events occur at the time scheduled for vaccination, the subject may be vaccinated at a later date, within the time window specified in the protocol (see Section 6.5), or the subject may be withdrawn from vaccination at the discretion of the investigator (see Section 9.5).

- Acute disease and/or fever at the time of vaccination.
  - Fever is defined as temperature  $\geq 38.0^{\circ}\text{C} / 100.4^{\circ}\text{F}$ . The preferred location for measuring temperature in this study will be the oral cavity.
  - Subjects with a minor illness (such as mild diarrhoea, mild upper respiratory infection) without fever can be administered study vaccines.

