## 11.4. Determination of sample size

The sample size determination enables the evaluation of the non-inferiority of HZ recurrence incidence rate, and to rule out a 5-fold increased risk of HZ recurrence in the HZ/su group compared to the placebo group. The following assumptions were made:

- Incidence rate of HZ recurrence in the placebo group= 0.55% per year.
- Incidence rate of HZ recurrence in the HZ/su group= 0.275% per year, assuming a 50% vaccine efficacy.
- Power of 90% and Type I error of 0.025 (one-sided).
- Criterion for non-inferiority = 5-fold; the 5-fold criterion has been selected as acceptable for ruling out a moderate increased risk of HZ in a clinical trial setting.

Let  $\pi$  be the ratio of incidence rate of HZ recurrence in HZ/su group vs the placebo group, then null hypothesis  $H_0: \pi \geq 5$  vs. alternative hypothesis  $H_a: \pi < 5$ . With the assumption that the number of HZ recurrence cases in HZ/su and placebo group follows Poisson distribution independently, conditioning on the total number of cases, the number of cases in HZ/su group would follow the binomial distribution [Lehmann, 1959]. With 1:1 randomization, the parameter  $p$  in the binomial distribution (that is, the probability of HZ recurrence in HZ/su group) is expected to be  $p=\pi/(1+\pi)$ . Therefore, the above hypotheses becomes:  $H_0: p \geq 0.8333$  vs.  $H_a: p < 0.8333$ . Under the assumption of VE of 50%, a total number of 10 HZ recurrence cases is needed (PASS 12: Tests for One Proportion using proportions (Exact Test)). With incidence rate of 0.55% per year and two year follow up, 606 evaluable subjects per group are needed. Further assuming a dropout rate of 15% during the 2 year follow up period, 713 subjects per group (a total of 1426 subjects) need to be enrolled.

CCI

A large black rectangular redaction box covers the majority of the page content below the CCI label, starting from the bottom of the CCI label and extending down to just above the section 11.4.2 header.

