2.2. Endpoints

2.2.1. Primary endpoints

[figure not shown]
- Occurrence of confirmed HZ episodes from 30 days post second vaccination until study end.

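### SAP 5.3.1.1 starts a within-group HZ window at the last vaccination and names only the ES, in conflict with the second-dose endpoint and the follow-up clocks in SAP 9.1.3

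*SAP*

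**What the plan says.** SAP 5.3.1.1, headed as a within-group analysis, plans a table of subjects, person-time, confirmed HZ cases and incidence rate for two windows. These "will be tabulated from 30 days post the last vaccination until study end and from first study vaccination until study end on ES". The ES is the only analysis set named in the sentence.

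The primary endpoint in SAP 2.2.1 is "Occurrence of confirmed HZ episodes from 30 days post second vaccination until study end", and Protocol 11.1 agrees. Protocol Appendix C records that Amendment 1 deliberately changed this anchor from the last to the second vaccination. The SAP's document history shows that its first version was written against Amendment 1. SAP section 8, which lists departures from the protocol, does not mention a return to the last vaccination.

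SAP 9.1.3 gives two start dates for time at risk: the dose 1 date for analyses on the ES, and 30 days after dose 2 for analyses on the mES. SAP 4.1.3 puts anyone with at least one dose in the ES.

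Protocol 7.5 lists "Occurrence of HZ between the first and second vaccine dose" among the absolute contraindications to further doses. Footnote 5 to Protocol Table 7 says of the two doses: "Any subject with a clinically diagnosed suspected HZ episode between Visit 1 (Day 1) and Visit 2 (Month 2) is not to receive the second".

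**The concern.** On the ES, *last* and *second* mean different things, and the outcome can decide which applies. A subject who develops HZ between the doses gets no dose 2, so dose 1 becomes that subject's last dose. If the case is confirmed and its onset is at least 30 days after dose 1, it falls inside the window that opens 30 days after the last vaccination. A subject who stays free of HZ over the same days receives dose 2, and that subject's clock opens only 30 days later. The case is in the numerator, but the event-free time over the same days is not in the denominator.

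The sentence also has no derivation behind it, because SAP 9.1.3 provides no clock starting 30 days after the last dose on the ES. A programmer would have to choose between following 5.3.1.1 and following 9.1.3. At stake is a descriptive rate that is somewhat too high, under a label very close to that of the primary endpoint.

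**Working it through.** **1. The plan's own figures (Protocol 11.4).** The inputs are "Incidence rate of HZ recurrence in the placebo group= 0.55% per year"; half that rate, 0.275% per year, for HZ/su; "Criterion for non-inferiority = 5-fold"; one-sided alpha 0.025; 90% power; 1:1 allocation. Conditional on total cases, p0 = 5/6 and p1 = 0.5/1.5 = 1/3.

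- With 10 cases, success is 5 or fewer in HZ/su: exact alpha 0.0155, power 0.923. With 9 cases the power is 0.855. Ten is the smallest total that reaches 90%.
- Evaluable per group: 10 / [2 × (0.0055 + 0.00275)] = 606.06, planned as 606.
- Enrolled per group: 606 / 0.85 = 712.9, planned as 713.

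All three figures reproduce, and none depends on the sentence in question.

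**2. The literal reading of the first window on the ES.** Let N = 713 per arm, r = the annual rate, d = the day of dose 2, and F = the days from d + 30 to study end. Dropout is ignored. Follow-up is 790 days from enrolment, the planned length for the last enrolled subject.

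- Cases added: N × r × (d − 30)/365.25
- Cases properly in the window: N × r × F/365.25
- Two-dose person-years left out between dose 1 + 30 days and dose 2: N × (d − 30)/365.25
- Relative inflation: approximately (d − 30)/F. N and r cancel. The added cases' own person-time is negligible: at day 60 it is 0.32 × 15/365.25 = 0.013 person-years.

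Placebo, r = 0.0055:

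| Dose 2 at | F (days) | Cases added | Person-years left out | Cases properly in window | Rate per 1000 person-years, literal vs correct | Inflation |
|---|---|---|---|---|---|---|
| Day 60 (optimal) | 700 | 0.32 | 58.6 | 7.52 | 5.74 vs 5.50 | 30/700 = 4.3% |
| Day 83 (end of standard window) | 677 | 0.57 | 103.5 | 7.27 | 5.93 vs 5.50 | 53/677 = 7.8% |
| Day 180 for everyone (upper bound) | 700 | 1.61 | 292.8 | 7.52 | 6.68 vs 5.50 | 150/700 = 21% |

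The last row uses F = 700 because Protocol Table 11 keeps at least 730 days from Visit 2 to the Month 26 contact for the last enrolled subject, even under the extended dose interval, and 730 − 30 = 700.

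A simulation of 2000 trials per scenario agrees: 5.77 vs 5.54 at day 60 (+4%) and 5.92 vs 5.49 at day 83 (+8%).

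**3. Longer follow-up.** Subjects enrolled early may be followed for longer, and Protocol 5.3 anticipates a maximum of about 4 years (1461 days). At that length the inflation is 30/(1461 − 90) = 2.2% for day 60 and 150/(1461 − 210) = 12% for day 180.

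**4. Effect on the ratio.** With the planned HZ/su rate of 0.00275 and dose 2 at day 60, 0.16 cases are added to 3.76. The ratio is (3.76 + 0.16)/(7.52 + 0.32) = 0.50, as planned. Under a constant effect both arms are inflated by the same factor.

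**The case against.** The strongest objection is that the literal reading is not the intended one. The phrase naming the ES closes the sentence and can belong to the second window alone. The first window would then be on the mES, which is the primary population. Every mES member has two doses, so last and second coincide and the problem disappears. The two clocks in SAP 9.1.3 match the two windows on exactly that reading. Both documents also use *last vaccination* loosely for dose 2, for example when they place Month 3 one month after it. This stands as far as it goes: the documents do not settle that cases will be counted in the literal way. It does not rescue the sentence, which names one set for two windows and keeps a term that the protocol had corrected.

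A reader might infer more: that a between-dose excess of HZ would distort the comparison of arms. For instance, assuming a 5-fold HZ/su rate between doses and no excess afterwards, this row would show (700 + 5 × 30)/(700 + 30) = 1.16 at day 60 instead of 1.0. The documents do not support that as a consequence for the trial. The 5-fold scenario is an assumption. The table is within-group, and no formal test uses this window. The primary test is on the mES, which removes confirmed HZ before 30 days after dose 2. The ES repeat runs on the dose 1 clock, with between-dose cases and their person-time both counted. The same 5.3.1.1 sentence also tabulates from first vaccination, so between-dose cases stay visible.

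A reader might also put the day-180 inflation at 150/580 = 26%, by ending follow-up at day 790 after a 180-day delay. That pairs the longest delay with the shortest follow-up, contrary to the interval from Visit 2 in Protocol Table 11.

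**Conclusion.** The point holds as an unreconciled conflict between SAP 5.3.1.1 and both SAP 2.2.1 and 9.1.3. It does not hold as a flaw in the primary analysis. If 5.3.1.1 is programmed literally on the ES, the first row's rate is too high by about 4% with dose 2 at day 60 and about 8% at day 83. The upper bound is about 21% if every dose 2 came at day 180, and it shrinks as follow-up lengthens. At the 60-day interval the expected number of misplaced cases is below one per arm: 0.32 placebo and 0.16 HZ/su.

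These figures assume the protocol's rates, constant over time within each arm, 713 per arm, no dropout, and the follow-up stated in the working. Only confirmed cases with onset at least 30 days after dose 1 count. Earlier HZ also stops dose 2 but adds nothing to this row. The mES non-inferiority test, its repeat on the ES, and the planned 10 cases, 606 and 713 subjects are unaffected.

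**What to change.** In SAP 5.3.1.1, give each window its own analysis set and start: on the mES, from 30 days after the second dose to study end; on the ES, from dose 1 to study end. Drop the window that starts 30 days after the last dose on the ES. This matches SAP 2.2.1 and the clocks in 9.1.3, and the ES row still shows between-dose cases with their full person-time. The cost is one SAP sentence. It needs no new data and no derivation beyond what 9.1.3 already defines.

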5.3.1.2. Between group

A formal non-inferiority analysis with a non-inferiority margin of 5 will be performed. Non-inferiority assessment will be carried out based on the fact that the distribution of two Poisson variates conditional on their sum is binomial [Lehmann, 1959]. Let n_1 and n_0 be the number of HZ recurrence cases, T_1 and T_0 (years) be total follow up, and r_1 and r_0 be the incidence rate in HZ/su group and placebo group respectively. It is assumed that $n_i \sim \text{Poisson}(\lambda_i)$ ($i=0,1$) and $\lambda_i = T_i \times r_i$, and condition on $n = n_0 + n_1$, $n_1 \sim \text{Binomial}(n, p)$, where $p = \lambda_1 / (\lambda_1 + \lambda_0)$. A 95% exact CI for p can be derived by using Clopper-Pearson approach, through which a 95% exact CI for $\pi = r_1 / r_0$ (that is, the ratio of incidence rate of HZ recurrence (HZ/su versus placebo)) can be derived. Non-inferiority is met if the upper limit of the 95% CI for π is below 5.

In addition to performing a formal non-inferiority analysis, to further quantify the likelihood of the risk increase of HZ following *Shingrix* vaccination, a probability curve that the ratio of incidence of HZ recurrence (HZ/su versus placebo) is higher than x -fold (x varying from 1 to 5) will be estimated by Bayesian methodology. It will be assumed that the number of HZ cases in the HZ/su and in placebo groups follows Poisson distribution with rate (incidence rate) of λ_{HZ} and λ_P respectively. We further assume that λ_{HZ} and λ_P are random variables both with non-informative Gamma prior distribution: Gamma (0.001, 0.001). Based on the posterior distribution of λ_{HZ} and λ_P , the probability curve of the ratio of incidence of HZ recurrence (HZ/su versus placebo), that is, $\text{Pr}(\lambda_{HZ}/\lambda_P > x | \text{data, prior})$, can be calculated for each given value of x .

5.3.2. Additional considerations

For analysis for non-inferiority, only the first confirmed HZ episode will be considered. The non-inferiority will be assessed by following model and fitted via the PROC GENMOD procedure according to the following code:

```
PROC GENMOD data=XXX;
  CLASS group_nb(ref="Placebo") / param=ref;
  MODEL nb_cases = group_nb / dist=poisson offset=log_T link=log type3;
```

```

EXACT group_nb / estimate=odds;
ODS OUTPUT ExpExactParmEst=IRR;
RUN;

```

where,

nb_case = number of cases

Group_nb = Group information of the subject (treatment received by subject)

Log_T = Log of the follow-up time

Note: variables names may vary as per ADAM variables however their derivations remain the same.

The estimated rate ratio and its 95% CI will be provided in the output dataset IRR.

In extreme situations, when there are no confirmed HZ cases in the HZ/su group and > 0 confirmed HZ cases in the Placebo group, the EXACT computational algorithm used in SAS will run into difficulty and cannot provide accurate results. Therefore, the rate ratio (HZ/su versus placebo) will be set to 0. When there are no confirmed HZ cases in the Placebo group and > 0 confirmed HZ cases in the HZ/su group, the rate ratio is not estimable, instead the incidence rate and 95% CI in each treatment group will be reported.

- For Bayesian analysis, the number of HZ cases in the HZ/su and in placebo groups follows Poisson distribution with rate (incidence rate) of λ_{HZ} and λ_P , respectively. We further assume that λ_{HZ} and λ_P are random variables both with non-informative Gamma prior distribution: Gamma (0.001, 0.001). The posterior distribution of λ_{HZ} and λ_P will be Gamma distribution with parameter

$\lambda_{HZ} \sim \text{Gamma}(0.001 + case_{HZ}, 0.001 + T_{HZ})$ and

$\lambda_P \sim \text{Gamma}(0.001 + case_P, 0.001 + T_P)$

where,

$case_{HZ}$ = number of cases in HZ/su group

$case_P$ = number of cases in placebo group

T_{HZ} = total follow-up time in years in HZ/su group

T_P = total follow-up time in years in placebo group

To estimate the probability of incidence rate ratio, simulation program will be run to generate sample from Gamma distribution using the function above.

The probability of incidence rate ratio greater than a specified value (e.g., 1, 2, 3, 4, 5) will be plotted against incidence rate ratio in graph.

In extreme situations, when there are no confirmed HZ cases in the HZ/su group or the Placebo group, the Gamma prior distribution will be updated to Gamma (0.015, 0.015), considering the minimum acceptable alpha in SAS is 0.015.

Considering the enrolment gap due to COVID-19, if data permit, the following sensitivity analyses will be conducted to explore between group comparisons to complement the analysis of primary endpoint:

- *A sensitivity analysis comparing HZ incidence rates between HZ/su and placebo groups on adopted mES removing the participants who received a second dose more than 2 months after the first dose (outside of the original scheduled window receiving the second dose >83 days after the first dose).*
- *A sensitivity analysis comparing HZ incidence rates between HZ/su and placebo groups stratified by enrolment pre- and post- recruitment interruption, using March 14th 2020 (the first day of site closure) as the cut-off date.*
- *Kaplan-Meier curves to compare the onset time of HZ recurrences since receipt of the first and second assigned dose.*
- *Moreover, if very different distribution between the HZ/su group and placebo group is presented, the Kaplan-Meier analysis on appropriate subintervals may also be performed.*

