1. DOCUMENT HISTORY

Date	Description	Protocol Version
28 AUGUST 2019	First version	Amendment 1: 18 MAR 2019
24 JANUARY 2020	Amendment 1: amendment of the SAP definition of enrolled set to better align across study documents, specifically the protocol and eCRF completion guidelines. None of these modifications are major changes to planned analysis.	Amendment 1: 18 MAR 2019
06 Oct 2023	
Amendment 2:
 
The protocol was amended to include subjects vaccinated beyond the original 2-month dose interval during the special circumstances of the COVID-19 pandemic. Per CHMP Scientific Advice received on March 24, 2022, the SAP is amended to add a sensitivity analysis for non-inferiority after removing the participants who received a second dose more than 2 months after the first dose (outside of the original scheduled window), a stratified analysis for non-inferiority by recruitment interruption, and Kaplan-Meier curves to compare the onset time of HZ recurrences.
 
Added clarifications on how to handle extreme cases, when there are no confirmed HZ cases in one of the treatment groups.
 
Added analysis to assess the impact of COVID-19 on safety.
	Amendment 2: 14 APR 2020

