6. ANALYSIS INTERPRETATION

The primary objective of non-inferiority of the incidence of HZ recurrence in the HZ/su and placebo groups is considered met if the upper limit of the 95% CI of the ratio of the incidence of HZ recurrence (HZ/su versus placebo) is below 5.

For all secondary objectives, analyses will be descriptive with the aim to characterize the differences in reactogenicity, safety and immunogenicity between groups.

The ratio of incidence of HZ recurrence (HZ/su versus Placebo) calculated using Bayesian methodology will be a descriptive analysis to provide additional information about incidence rate ratio between Hz/su and Placebo based on simulated data with assumption provided (sections [5.3.1.2](#) and [5.3.2](#)) of the SAP.

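### With no cases in the HZ/su group, does setting the rate ratio to 0 leave the primary criterion without an upper limit to test?

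*SAP*

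**What the plan says.** **Criterion.** SAP 6 counts the primary objective as met if "the upper limit of the 95% CI of the ratio of the incidence of HZ recurrence (HZ/su versus placebo) is below 5". Protocol 2.1 and 11.11 and SAP 2.1.1 state the same rule.

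**Method.** SAP 5.3.1.2, repeating Protocol 11.8, conditions on the total number of cases, so that the HZ/su count is binomial. It then says "A 95% exact CI for p can be derived by using Clopper-Pearson approach", and the limits for p are converted to limits for the rate ratio.

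**Implementation.** SAP 5.3.2, headed as additional considerations, gives PROC GENMOD code with an EXACT statement: "The estimated rate ratio and its 95% CI will be provided in the output dataset IRR".

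**Empty group.** SAP Amendment 2 brought in a rule for this; the document history reads "Added clarifications on how to handle extreme cases, when there are no confirmed HZ cases in one of the treatment groups". With no HZ/su cases and some placebo cases, SAP 5.3.2 says that "the EXACT computational algorithm used in SAS will run into difficulty and cannot provide accurate results", and goes on: "Therefore, the rate ratio (HZ/su versus placebo) will be set to 0". With no placebo cases and some HZ/su cases, it says that "the rate ratio is not estimable, instead the incidence rate and 95% CI in each treatment group will be reported".

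**The concern.** The criterion needs an upper limit, and the empty-HZ/su rule supplies a point value. SAP 5.3.2 names the GENMOD output as the source of the interval, declares that output inaccurate in this situation, puts 0 in its place, and does not point back to SAP 5.3.1.2. The gap stands out because the opposite branch, in the same paragraph, does say which intervals to report. Nor do the other interval sections help: SAP 9.2.1 covers single-group rates and SAP 10.1.5.1 covers within-group proportions.

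A ratio of 0 looks like success whatever the placebo count. If a programmer reported it with no limit and a reader took it as meeting the criterion, non-inferiority could be claimed on one or two placebo cases, where the exact limit is above 5. The branch could also be entered often if the vaccine worked as well here as in the earlier efficacy trials.

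**Working it through.** **1. The plan's own figure.** Inputs from Protocol 11.4: margin 5, one-sided alpha 0.025, power 90%, placebo rate 0.55% per year, and "Incidence rate of HZ recurrence in the HZ/su group= 0.275% per year, assuming a 50% vaccine efficacy". With 1:1 allocation, p = 5/(1+5) = 0.8333 at the margin and p = 0.275/(0.275+0.55) = 1/3 under the planning assumption.

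- With 10 cases, the exact test rejects at 5 or fewer HZ/su cases: alpha 0.0155, power 92.3%. Nine cases give 85.5%, so 10 is the smallest total reaching 90%.
- Evaluable per group: 10 / [2 × (0.0055 + 0.00275)] = 606.06, so 606. Enrolled: 606/0.85 = 712.9, so 713.

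The stated figures reproduce, using the same conditional binomial as SAP 5.3.1.2.

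**2. The limit with no HZ/su cases.** Let n0 be the placebo cases, and T1 and T0 the follow-up in HZ/su and placebo. Clopper-Pearson gives p_U = 1 − 0.025^(1/n0). Converting to the ratio:

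UL = (T0/T1) × p_U/(1 − p_U) = (T0/T1) × (0.025^(−1/n0) − 1)

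For n0 = 2 and equal follow-up: 0.025^(−1/2) = √40 = 6.325, so UL = 5.32. As a check, the exact one-sided p-value at a ratio of 5 is (1/6)^n0, to be compared with 0.025.

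| Placebo cases | UL | (1/6)^n0 | UL below 5? |
|---|---|---|---|
| 1 | 39.0 | 0.167 | no |
| 2 | 5.32 | 0.0278 | no |
| 3 | 2.42 | 0.0046 | yes |
| 4 | 1.51 | 0.0008 | yes |
| 7 | 0.69 | below 0.0001 | yes |

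The two columns agree in every row.

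**3. Effect of unequal follow-up.** The decision changes where T0/T1 equals 5 divided by the equal-follow-up limit: 5/39 = 0.13 for one placebo case, 5/5.3246 = 0.939 for two, 5/2.42 = 2.07 for three. Only two placebo cases are sensitive to a modest imbalance (T0/T1 = 0.90 gives 4.79; 1.10 gives 5.86). SAP 5.3.1.2 carries T1 and T0 in its formula and SAP 9.1.3 defines follow-up time, so this is settled by the data.

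**4. How often it arises.** Independent Poisson counts, 606 per group for two years. Placebo mean: 606 × 2 × 0.0055 = 6.67. HZ/su mean: 6.67 × (1 − VE). At 50% efficacy:

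- P(no HZ/su cases) = exp(−3.333) = 0.0357
- P(at least one placebo case) = 1 − exp(−6.666) = 0.9987; product 3.6%
- P(one or two placebo cases) = exp(−6.666) × (6.666 + 6.666²/2) = 0.0368; product 0.13%

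| Efficacy | HZ/su mean | 0 HZ/su, placebo ≥ 1 | 0 HZ/su, placebo 1 or 2 |
|---|---|---|---|
| 50% (plan) | 3.33 | 3.6% | 0.13% |
| 89.8% | 0.68 | 51% | 1.9% |
| 97.2% | 0.19 | 83% | 3.1% |

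The last two rows borrow the efficacy quoted in Protocol 1.1. They are illustrative, since Protocol 1.2.1 notes that most of the earlier studies excluded people with previous HZ.

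Ranges under further assumptions, for the last column:

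- Mean follow-up of 3 years at 0.55% per year: 0.002%, 0.10% and 0.21%.
- Half the planned placebo rate (0.275% per year) for 2 years: 6.0%, 23% and 29%.
- Half the rate for 3 years, at the two higher efficacies: 7.1% and 10.3%; for 4 years, 1.9% and 3.1%.

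Two years is close to the minimum. Under Protocol 3, subjects enrolled early are followed for longer than the last one, and Protocol 5.3 allows for about four years.

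**5. Which text governs.** The GENMOD model has a single group term. Its exact analysis conditions on the total number of cases, so it works from the binomial of SAP 5.3.1.2; the code is a way of computing that interval. SAP 8, which lists departures from the protocol analysis, records no change to the interval method or the criterion. When the software fails, the method it was meant to compute still stands, and by step 2 it needs one line of arithmetic.

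**The case for a change.** The strongest reply is that SAP 5.3.2 does more than supply code. It states that non-inferiority will be assessed with that model, declares the model unusable here, and prescribes a substitute that is not the Clopper-Pearson limit. The rule was written on purpose for this situation, late in the trial, and still omits the number that decides the objective. With two placebo cases the choice of limit matters: a one-sided 95% limit would be 3.47 and would pass, while the two-sided 95% limit is 5.32 and fails. One sentence would close the gap at almost no cost.

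The omission is real, and the sentence would be helpful. The choice of limit is not open, though: the plan asks for a 95% interval by Clopper-Pearson, and Protocol 11.4 sets one-sided alpha at 0.025, which puts 0.025 in the upper tail. Nor does any section let a point estimate decide; every statement of the criterion refers to an upper limit. The 51% and 83% are chances of entering the branch. Given entry with at least one placebo case, the chance of only one or two is 0.0368/0.9987 = 3.7% at the planned placebo rate and two years, whatever the efficacy. The larger joint figures of 23% and 29% need half the planned placebo rate, efficacy carried over from another population, and near-minimum follow-up, all together.

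The reverse branch, with no placebo cases, cannot produce a false success: a ratio that cannot be estimated has no finite upper limit to fall below 5.

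**Conclusion.** No change follows. This is a gap in detail that the analysts fill from the preceding section of the SAP. Read as a whole, the plan fixes the method (two-sided 95% Clopper-Pearson on the conditional binomial), the follow-up adjustment and the decision rule, and all three work with zero HZ/su cases. The reported result would be a ratio of 0 with an upper limit of (T0/T1) × (0.025^(−1/n0) − 1). At about equal follow-up the objective is not met with one or two placebo cases and is met with three or more.

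A wrong conclusion would require someone to treat the point value as the test, against every statement of the criterion, and the placebo group to have exactly one or two cases. That data pattern has probability 0.13% at the planning inputs, and up to 3.1% if the earlier trials' efficacy carried over at the planned placebo rate and two years. It would be materially more likely only if the placebo rate were well below plan. These figures assume independent Poisson counts, 606 evaluable subjects per group and equal follow-up.
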